1. THE AIM OF THE STUDY

To develop a model of individualized risk of coronary heart disease outcomes and side effects of therapy based on clinical and instrumental, biochemical, and genetic parameters in patients with ACS.

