2. STUDY DESIGN AND PATIENT'S SELECTION

2.1. STUDY DESIGN

This is the Russian multicenter observational study of ACS patients with at least one-year follow-up. We planned to include 1700 ACS patients admitted to invasive hospitals. The follow-up will continue until at least 200 deaths for any reason.

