4.1.6. Coronary revascularization

Taking into account all the cases of revascularization procedures

5. COLLECTION AND ANALYSIS OF STATISTICAL DATA.

Statistical analysis was performed using a standard statistical package IBM SPSS Statistics Version 22 for Windows and MedCalc software version 18.3. It involves analysis of clinical predictors

- all cause mortality
- cardiovascular mortality
- all cardiovascular events
- stroke
- any, significant and major hemorrhage

For continuous variables will be analyzed and the distribution criteria for its compliance with the normal using the Kolmogorov-Smirnov test. To describe the features of the normal distribution using the mean with standard deviation

indication ($M \pm SD$). For signs with non-normal distribution when reporting the results indicate the median and interquartile range - the 25th and 75th percentiles ($Me (Q1-Q3)$). Discrete values are calculated as a percentage, the significance of differences were compared by Pearson criterion χ^2 . Comparison of quantitative traits obeying the normal distribution, is carried out using t-criterion Student, unnormal distribution - by using the non-parametric test, the Mann - Whitney and Kruskal - Wallis test for unrelated groups. For quantitative evaluation of the values calculated correlation coefficient is obtained and the accuracy depending on the Pearson's criteria (normal distribution) or Spearman (with a deviation from the normal distribution) for bilateral hypothesis testing criterion. The rating values of the predictor is conducted by plotting ROC curve and calculating the area under the curve (AUC). Treatment Evaluation of Frequency Allocations alleys and genotypes studied these genes will be performed using "Gene Expert" unified program. Genotype frequency distribution was calculated (the Hardy-Weinberg equilibrium test), genetic risk of NO using multiplicative general, dominant and recessive inheritance models. To assess the effect of clinical factors on the independence of the risk of adverse outcomes is performed using the Kaplan-Meier method using the log-rank test (Log Rank) and using Cox regression.

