The regression analysis Univariate Cox included parameters are different when the comparative analysis between the groups of patients with a favorable and unfavorable outcome. The development of prognostic functions performed by using multivariate logistic regression. For all types of analysis were considered statistically significant value of $p < 0,05$.

It is supposed to analyze the prognostic data for specific groups of patients:

- patients 75 years and older
- patients with "early" debut atherosclerosis (men younger than 55 years, women younger than 60 years)
- patients with diabetes
- patients with CKD

7. ETHICAL AND LEGAL ASPECTS.

7.1 Informed consent of the patient.

Patients who meet all eligibility criteria, are considered suitable. Before inclusion in the clinical study of the patient must provide written consent to participate in the study, after the nature of the study will be explained verbally and in writing. Patients should be informed that in the course of study they will have taken blood for research purposes, including for genetic analysis.

7.2 The principle of confidentiality.

The data obtained from the study, and stored in the computer must be protected, as required by the law on personal data protection. The researchers will treat all personal information about the patient obtained during the investigation, in full respect of medical confidentiality and personal data protection law.

8. DATA OWNERSHIP AND USE OF RESEARCH RESULTS.

Each research group has the right to publish their own data, obtained as a result of the study.

Publication and other use of materials produced in other centers, with the consent of researchers, guiding the work of the centers.

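### The individual risk model has no planned internal validation, calibration or shrinkage, so its AUC is expected to be too high and its predicted risks too extreme

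*Combined protocol and SAP*

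**What the plan says.** The aim in section 1 is: "To develop a model of individualized risk of coronary heart disease outcomes and side effects of therapy". The Introduction values such prediction because it would guide treatment of the individual patient, and it foresees a large set of clinical data together with many genotypes.

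The model-building plan is in section 5 (Collection and analysis of statistical data):

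- Screening: "The regression analysis Univariate Cox included parameters are different when the comparative analysis between the groups of patients with a favorable and unfavorable outcome".
- Independence of effects: Kaplan-Meier, log-rank and Cox regression, introduced by "To assess the effect of clinical factors on the independence of the risk of adverse outcomes".
- The model itself: "The development of prognostic functions performed by using multivariate logistic regression".
- Performance: an ROC curve and AUC for the predictor.
- Threshold: "For all types of analysis were considered statistically significant value of" p<0.05.

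The outcomes listed for analysis include all-cause death, stroke and "any, significant and major hemorrhage". Section 2.1 plans 1700 patients and fixes a minimum event count for deaths only: "The follow-up will continue until at least 200 deaths for any reason".

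Nothing in the document mentions a split sample, cross-validation, bootstrap, calibration, penalisation or shrinkage. It gives no rule by which variables enter or stay in the logistic model and no number of candidates. The earlier 1,200-patient cohort is background and has no validation role.

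**The concern.** A model whose variables are chosen and whose coefficients are fitted in one set of patients describes those patients better than it will describe new ones. An AUC taken from the same patients (the apparent AUC) is then too high. The coefficients are on average too large, so high predicted risks are too high and low ones too low. For a list of risk factors this might be tolerable. Here the intended product is a risk figure for one patient, so calibration is central.

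The problem grows with the number of candidates per event. Genetic markers examined under several inheritance models can raise the candidate count quickly. Outcomes other than death have no event minimum. The plan has no step that would show whether the resulting bias is trivial or serious.

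**Working it through.** **Inputs from the document.** 1700 patients and at least 200 deaths (section 2.1), so 200/1700 = 11.8%; a 0.05 threshold (section 5). The plan states no AUC, calibration slope or candidate count, and no derivation of the 1700 or the 200, so it has no figure of its own to reproduce.

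**Analytic check.** The largest number of parameters p that keeps expected shrinkage S at 0.9 is p = (S − 1) · n · ln(1 − R²/S), with R² on the Cox-Snell scale.

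- At 11.8% events the maximum Cox-Snell R² is 1 − exp{2[0.1176 ln 0.1176 + 0.8824 ln 0.8824]} = 0.515.
- Assumed Nagelkerke R² of 0.15: R² = 0.0773, and p = −0.1 × 1700 × ln(1 − 0.0773/0.9) ≈ 15.
- Assumed Nagelkerke R² of 0.25: R² = 0.1289, and p ≈ 26.

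With 200 deaths, about 15 to 26 candidate parameters can therefore be handled before expected shrinkage falls below 0.9.

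**Simulation of the plan.** Assumptions: 1700 patients, five true independent normal predictors with log-OR 0.4 per SD, the rest noise, and a between-group t-test screen at p<0.05. Under rule A every screened variable enters the logistic model. Under rule B, backward elimination to p<0.05 follows. Optimism is apparent AUC minus AUC in 20,000 new patients, over 200 runs per scenario (standard error 0.0012 to 0.0027). A slope below 1 means risks are too extreme.

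| Events | Candidates | Optimism A | Slope A | Optimism B | Slope B |
|---|---|---|---|---|---|
| 200 | 20 | 0.013 | 0.94 | 0.011 | 0.95 |
| 200 | 50 | 0.024 | 0.88 | 0.025 | 0.88 |
| 200 | 100 | 0.046 | 0.80 | 0.038 | 0.82 |
| 300 | 20 | 0.010 | 0.95 | 0.012 | 0.94 |
| 300 | 100 | 0.031 | 0.85 | 0.027 | 0.87 |
| 100 | 20 | 0.024 | 0.89 | 0.023 | 0.89 |
| 100 | 50 | 0.044 | 0.80 | 0.040 | 0.82 |
| 50 | 20 | 0.060 | 0.74 | 0.056 | 0.75 |

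Rule A, 200 deaths, with 20, 50 and 100 candidates:

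- In the top tenth of predicted risk, predicted against true risk is 33.5% v 32.1%, 34.3% v 31.5% and 35.5% v 30.4%.
- Noise variables make up 0.8 of 5.8, 2.2 of 7.1 and 4.8 of 9.8 selected variables.

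At 50 events and 20 candidates the top tenth is 10.5% predicted v 8.1% true.

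**Sensitivity at 200 deaths.**

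- Eight weaker true predictors (linear-predictor SD 0.9, true AUC about 0.73), screened, with 20, 50 and 100 candidates: optimism 0.020, 0.029, 0.047; slope 0.90, 0.86, 0.79.
- The same setup without any screen, 20 and 50 candidates: optimism 0.031 and 0.069; slope 0.84 and 0.68. The bias therefore does not depend on the screen feeding the logistic model.
- Eight true predictors at log-OR 0.5, screened, 50 and 100 candidates: optimism 0.017 and 0.027; slope 0.92 and 0.88.
- The five-predictor setup with pairwise correlation 0.3, 50 and 100 candidates: optimism 0.051 and 0.098; slope 0.76 and 0.59.

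**Test of the remedy.** Rule A, 200 further runs, with the whole procedure repeated in 100 bootstrap resamples:

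| Events, candidates | Apparent AUC | Bootstrap-corrected | Actual | Slope before → after shrinkage | Top tenth: before / after / true |
|---|---|---|---|---|---|
| 200, 20 | 0.734 | 0.714 | 0.722 | 0.94 → 1.04 | 33.8 / 31.6 / 32.2% |
| 200, 50 | 0.744 | 0.706 | 0.715 | 0.86 → 1.04 | 34.8 / 30.6 / 31.4% |
| 200, 100 | 0.751 | 0.688 | 0.706 | 0.80 → 1.08 | 35.6 / 29.0 / 30.2% |
| 50, 20 | 0.750 | 0.693 | 0.695 | 0.76 → 1.00 | 10.5 / 8.6 / 8.2% |

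Under rule B (100 runs) the slope moved from 0.94 to 1.03 (200 deaths, 20 candidates), 0.82 to 1.10 (200, 100) and 0.79 to 1.06 (50, 20). Ten-fold cross-validation repeated five times (rule A) gave AUCs of 0.720, 0.717 and 0.705 at 200 deaths with 20, 50 and 100 candidates, and 0.689 at 50 events, where its slope was unstable.

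**The case against.** **The reading is partly inferred.** The AUC sentence concerns a predictor rather than the final model, and the outcome-group screen is written for univariate Cox regression, not for the logistic model. Both points are correct, so the bias is an expectation on the natural reading, not a certainty. If the AUC is not meant for the final model, however, the plan has no performance measure for its main product.

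**The size is assumed.** Candidate counts, effect sizes, correlation and the 50- and 100-event cases are not in the document. No sentence says that a function will be built for stroke or haemorrhage, although the aim includes side effects of therapy. The 200 deaths are a minimum, and more would reduce the bias. This stands: the sensitivity runs show the size moving both ways, and only the direction is robust.

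**The remedy is imperfect.** At 200 deaths the bootstrap-corrected AUC errs low by 0.008, 0.009 and 0.018, and cross-validation is closer. Shrinkage overshoots slightly. This also stands, but every corrected AUC shown is nearer the actual value than the apparent one, and every shrunken slope is nearer 1 than the unshrunken one.

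**Validation could be added at analysis anyway.** It could, and no information would be lost. That limits the severity but does not remove the gap. The time horizon to which a predicted risk refers is a separate matter.

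**Conclusion.** The concern holds and should be fixed; confidence is moderate. The omission is a fact of the text. In every setting tried, the apparent AUC exceeded the AUC in new patients and the mean calibration slope was below 1.

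Under the five-predictor assumptions with 200 deaths, the bias is small at 20 candidates (optimism 0.011 to 0.013, slope about 0.94). It becomes material at 50 to 100 candidates (optimism 0.024 to 0.046, slope 0.88 to 0.80). It is also material for a rarer outcome, if a function is built for one (about 0.06 and 0.75 at an assumed 50 events with 20 candidates). Stronger predictors reduce these figures and correlated ones raise them. Which case applies cannot be known until the candidate count is stated.

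**What to change.** Add to section 5, next to the sentence on logistic regression:

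1. The rule by which variables enter and stay in the logistic model, and the number of candidates, counting each genetic coding. Keep that number modest relative to events.
2. Repetition of the entire procedure, from group comparison to final fit, in at least 500 bootstrap samples.
3. The optimism-corrected AUC, the calibration slope and a calibration plot, reported as the model's performance.
4. Multiplication of the final coefficients by the bootstrap slope, with the intercept re-estimated.
5. If about 50 or more candidates are screened at around 200 events, repeated 10-fold cross-validation of the same procedure as well, because the bootstrap AUC errs low there. The bootstrap slope is kept for shrinkage.

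The existing screen may stay. A pre-specified variable list or a penalised model is optional, since neither was shown here to be better on its own.

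**Cost.** SAP wording and extra programming, possibly outside SPSS and MedCalc; no new patients or data. The reported AUC will fall. In the simulation the fall at 200 deaths was about 0.02, 0.04 and 0.06 with 20, 50 and 100 candidates, and about 0.06 at 50 events with 20 candidates. Part of that fall is over-correction. At 20 candidates and 200 deaths the gain is modest.

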In the previous part of the study, the sample of patients of Moscow, St. Petersburg, Kazan, Chelyabinsk, Stavropol, Perm, and Rostov-on-the-Don was formed, of 1,200 people admitted due to acute coronary syndrome (ACS) including unstable angina and acute myocardial infarction, at coronary care units with follow-up for three years. We found several factors, including genetic, that significantly affect the outcomes of the disease. Coronary atherosclerosis and its complications now considered as a multifactorial disease associated with inherent factors. Therefore, the project provides, besides accounting a significant amount of clinical and instrumental data, the determination of a wide range of genotypes and alleles of polymorphic markers candidate genes encoding the protein factors of the hemostatic system, enzymes of lipid metabolism system, and anti-inflammatory cytokines. It is assumed that the prediction outcomes of coronary heart disease should be carried out taking into account the fact that several factors (gender, diabetes, age, aortic stenosis, atrial fibrillation, etc.) can not only significantly change the forecast itself but also affecting the significance of other risk factors. Since the last study, the standards significantly of ACS management changed. Invasive treatment not only creates opportunities to reduce coronary mortality but also increased demands on the patient's adherence to the assigned medication and creates additional risks associated with its activity (especially with an antithrombotic treatment activity). In these circumstances, the development of personalized approaches to prescribing drugs is particularly important. Thus, the prediction of coronary heart disease outcomes after an ACS on a set of clinical, instrumental, biochemical and genetic indicators is of great importance, as it allows to plan the most optimal treatment for the individual patient.

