5.2. Secondary end-points

1. cardiovascular (atherothrombotic) events (cardiovascular death, non-fatal myocardial infarction, non-fatal stroke)
2. non-fatal myocardial infarction
3. recurrent acute coronary syndrome (all cases of recurrent myocardial infarction or unstable angina after the index events)
4. recurrent PCI (all cases of recurrent PCI after the index hospitalization)
5. complicated atherosclerosis
6. non-fatal stroke

5.3 Other Pre-specified Outcome Measures:

1. Bleeding

all cases of bleeding during and after the index hospitalization

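### An unadjusted p < 0.05 covers an unspecified number of genetic markers under several inheritance models, with no rule for the family of tests and no exploratory label

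*Combined protocol and SAP*

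**What the plan says.** The threshold is in the statistical section (Collection and analysis of statistical data): "For all types of analysis were considered statistically significant value of" p < 0.05. The section has no other significance rule.

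The tests it governs are described in several places:

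- The Introduction plans "the determination of a wide range of genotypes and alleles of polymorphic markers candidate genes" in haemostatic, lipid and cytokine pathways. It gives neither a list nor a number.
- The statistical section plans "genetic risk of NO using multiplicative general, dominant and recessive inheritance models". This can be read as three models or four, none is named as deciding, and the outcome abbreviation is not defined.
- The same section lists five outcome items (the last with three grades of haemorrhage) and four patient subgroups.
- Section 2.1 gives the size: "We planned to include 1700 ACS patients admitted to invasive hospitals", and "The follow-up will continue until at least 200 deaths for any reason".
- Section 4.1 names all-cause death as the single primary endpoint but does not tie it to the genetic tests.

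Genetics is part of the stated aim, a model of "individualized risk of coronary heart disease outcomes and side effects of therapy based on clinical and instrumental, biochemical, and genetic parameters". The documents contain no multiplicity adjustment, false discovery rate rule, testing order or replication set, and do not call the genetic analysis exploratory.

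**The concern.** When many markers are each tested at 0.05, some with no effect will reach significance. Under the stated rule they would be called significant in the same terms as real ones. The Introduction says of the earlier 1,200-patient cohort: "We found several factors, including genetic, that significantly affect the outcomes of the disease". Some markers may therefore be real, but a reader of the results would have no means of telling which.

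The choice of inheritance model adds to this. If a marker counts as positive whenever any model reaches p < 0.05, its own error rate exceeds 5%.

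What is at stake is the credibility of the genetic risk factors that the study reports and, if genotypes follow the same selection route as other variables, the content of the risk model.

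**Working it through.** **Plan's own figure.** There is none to reproduce. The 0.05 is declared, not derived, and the 1700 patients and 200 deaths come without a power statement, effect size or marker count. Marker counts, allele frequencies and effects below are assumptions. Death is taken as the outcome because it is the primary endpoint.

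**Step 1: one model per marker, all markers null and independent.** P(at least one false marker) = 1 − 0.95^m.

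- m = 10: 1 − 0.95^10 = 0.401
- m = 20: 1 − 0.95^20 = 0.642
- m = 30: 1 − 0.95^30 = 0.785

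The chance passes 50% at ln 0.5 / ln 0.95 = 13.5, that is, 14 markers. The expected number of false markers is 0.05m, or 1 for m = 20.

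**Step 2: any of three models may decide.** Null genotypes were simulated in Hardy-Weinberg proportions for 200 deaths and 1500 survivors (1700 − 200) and tested under the per-allele, dominant and recessive models. At least one p < 0.05 occurred for r = 0.092 to 0.104 of null markers, over allele frequencies 0.1 to 0.5. A general two-degree-of-freedom test as a fourth model gives about 9–11%. With 1 − (1 − r)^m:

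| Null markers | One model | Any of three |
|---|---|---|
| 10 | 40% | 62–67% |
| 20 | 64% | 85–89% |
| 30 | 79% | 94–96% |

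The 50% point is ln 0.5 / ln(1 − r) = 6.3 to 7.2, that is, 7 to 8 markers.

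**Step 3: some markers real.** Survival was simulated for 1700 patients with follow-up stopped at the 200th death, 20 independent markers at allele frequency 0.3, and 1 or 3 true markers with a per-allele hazard ratio of 1.3. The table gives the mean share of declared markers that are false.

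| True markers | Rule | Studies declaring nothing count as 0 | Only studies declaring something |
|---|---|---|---|
| 1 | One model, p < 0.05 | 44% | 49% |
| 1 | Any of three, p < 0.05 | 64% | 66% |
| 1 | Per-allele, Benjamini-Hochberg 5% | 5% | 13% |
| 3 | One model, p < 0.05 | 25% | 25% |
| 3 | Any of three, p < 0.05 | 39% | 39% |
| 3 | Per-allele, Benjamini-Hochberg 5% | 4–5% | 6% |

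The two columns differ most for the adjusted rule with one true marker, because most such studies declare nothing: 5/13 is about 0.38, so roughly six in ten are empty. The last column is what a reader of a declared marker faces.

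**Step 4: route into the risk model.** The statistical section sends parameters that differ between outcome groups to univariate Cox regression and builds the prognostic function by multivariable logistic regression. It introduces its outcome list, and its Kaplan-Meier and Cox analyses, in terms of clinical predictors or factors. The aim requires genetic parameters in the model, but no sentence says that genotypes pass through this screen.

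**The case against.** The strongest case on the other side has four parts.

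**The study is observational and aims at prediction.** Strict family-wise control is not required for that purpose, and penalised modelling with validation could protect the model instead. This stands as far as it goes, and it is why a false discovery rate rule is proposed rather than Bonferroni. But the plan does not call the genetic analysis exploratory, and it applies a significance rule to it.

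**The percentages rest on assumptions.** This stands. The marker count is not given, the Step 1 and 2 figures take every marker as null, and linkage between markers would lower the chance of at least one false result. Linkage would not lower the expected number, 0.05m.

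**Control is not absent.** A reader might infer that false positives are wholly uncontrolled. The documents do not support that: each test is held at 5%, and only the family is open. Nor does the plan say that the best of several models decides. That is one reading, and the concern holds with a single model.

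**The risk model may not be affected.** A reader might infer that false markers will enter the individual risk model. Step 4 shows that the route is not stated, so this remains conditional. If genotypes do take that route, multivariable adjustment for other covariates does not correct for having screened many markers.

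**Conclusion.** The point holds for genetic association claims. A stated blanket rule, applied to many markers and several models, would lead to null markers being declared alongside real ones, and nothing in the documents limits or labels this. About 14 independent null markers are enough for an even chance of at least one false declaration with one model.

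With 20 assumed markers of which one is real (hazard ratio 1.3), about half of what is declared under one model would be false on average, against about 13% after adjustment, among studies that declare something. A reader might take the 5% in Step 3 as the false share among reported markers. It is not, because it counts empty studies as error-free.

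These sizes depend on the assumed marker count, independence, allele frequency and effect, and on death as the outcome. The existence of the problem depends only on there being more than a handful of markers, which the Introduction makes plain. This is a cheap improvement to the plan, not a defect of the design. Validation or penalisation of the prediction model is a separate matter.

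**What to change.** For genetic association with the primary endpoint, all-cause death, replace the blanket threshold with wording such as:

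> The markers are listed before analysis. Each has one deciding test in Cox regression, named in advance: per-allele, or the maximum over the inheritance models with its correct null distribution. Benjamini-Hochberg false discovery rate control at 5% is applied across the listed markers, and a marker is called a risk factor only on the adjusted result. Other inheritance models, outcomes and subgroups are reported with estimates, confidence intervals and unadjusted p-values and labelled exploratory, unless a further outcome family is named in advance and the same control is applied within it. Unadjusted p < 0.05 in the screen alone does not admit a genotype to the multivariable model.

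Presence on the list should not by itself admit a marker to the model, since every tested marker is listed. The sponsor may name coronary outcomes or bleeding as further families, as the aim would allow.

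**Cost.** SAP wording and little computing; no new patients, visits or data. The maximum test may need a short permutation routine. All univariate estimates remain reported.

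The downside is fewer declared markers. Power per true marker, under the Step 3 assumptions:

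| True effect | One model, 0.05 | Any of three, 0.05 | Per-allele, adjusted |
|---|---|---|---|
| Per-allele 1.3 (1–3 true) | 70% | 76–77% | 31–38% |
| Per-allele 1.5 (1 true) | 97% | 98% | 82% |
| Recessive 2.0 (1 true) | 66% | 91% | 30% |

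All figures are approximate. The 200 deaths are a minimum, so more deaths would soften the loss. For the recessive effect, the maximum test keeps a little over 60%, but at a per-allele hazard ratio of 1.3 it gives about 28–33%. The per-allele test is therefore the better choice only where additive effects are expected, and the choice should be made in advance.
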